4.1. Visits and Day Ranges

Since it is not always possible for all study participants to come in for their clinic visits on the exact day specified in the protocol schedule, the ‘Week’ of a subject visit will be defined by the following relative day ranges.

Visit	Target	Study Days
Baseline	Day 1	Day 1
Phone 1	Day 8	Days 2 to 10
Week 2	Day 15	Days 11 to 25
Phone 4	Day 29	Days 26 to 32
Week 6	Day 43	Days 33 to 53
Phone 8	Day 57	Days 54 to 64
Phone 10	Day 71	Days 65 to 74
Week 12 (EOT)	Day 85	Days 75 to 93
Week 16 (EOS)	Day 113	Days 94 to 127

4.2. Sample Size

A sufficient number of subjects (36 estimated) will be enrolled to ensure that 30 evaluable subjects complete 12 weeks of treatment. Subjects will be randomly assigned to the 3 OV101 total daily dosing regimens in a 1:1:1 ratio, stratified by age group (adolescents/adults), with a target ratio of 1:1 between adolescents and adults.

The main emphasis in reporting the data will be on descriptive statistics and estimation with 95% confidence intervals (CIs).

For the objective of estimating the overall subject incidence of TEAEs (for the 3 OV101 total daily dose arms combined), the precision varies with true incidence, e.g., a true incidence of 20% would be estimated with a 13.9% precision (half-width of the 2-sided 95% CI, assuming N = 30). Table 2 contains the estimated precision for different incidence rates, using the Wilson method of calculating a confidence interval for a binomial proportion.

Table 2 Incidence Rates and Corresponding Precision

True TEAE Incidence Rate	10%	13.3%	20%	23%	30%
Expected n with a TEAE (N=30)	3	4	6	7	9
Expected proportion, p	0.100	0.133	0.200	0.233	0.300
95% CI	(3.5%,25.6%)	(5.3%,29.7%)	(9.5%,37.3%)	(11.8%,40.9%)	(16.7%,47.9%)
Precision (half-width of CI)	11.1%	12.2%	13.9%	14.6%	15.6%

Note: All CIs are 2-sided and 95% CIs are calculated using Wilson's method.

Abbreviations: n, number of subjects observed; N, total number of evaluable subjects in the study (all treatment groups); TEAE, treatment-emergent adverse event.

4.3. Stratification, Randomization, and Blinding

An interactive web response system (IWRS) will be used to administer the randomization schedule. The study will be performed in a double-blind manner, with the subjects, LAR/caregivers, investigators, study personnel, monitors, and study sponsor blinded to the identity of all study drug.

Subjects who meet all eligibility criteria will be randomly assigned at Baseline to the 5 mg/day, 10 mg/day, or 15 mg/day OV101 treatment group in a 1:1:1 allocation ratio. It is anticipated that approximately 36 male subjects will be enrolled (to obtain 30 evaluable subjects), while maintaining a 1:1 target ratio between adolescents (13 to 17 years old, inclusive) and adults (18 to 22 years old, inclusive). The randomization schedule will be stratified by age (13 to 17, inclusive; 18 to 22, inclusive). It will also use an appropriate block size, which will not be revealed.

4.4. Analysis Set

Randomized Analysis Set: The randomized analysis set will consist of all randomly assigned subjects. This will be used for summaries of subject disposition, demographics, and other baseline characteristics.

Full-Analysis Set (FAS): The FAS will consist of all randomly assigned subjects who receive at least 1 dose of study drug and have at least 1 postbaseline efficacy assessment. Following

the intent-to-treat principle, subjects will be analyzed according to the treatment they are assigned to at randomization, regardless of compliance or any deviations from the study protocol. All efficacy evaluations will be carried out on the FAS.

Safety Set: The safety set will consist of all subjects who receive at least 1 dose of study drug. All analyses using the safety set will group subjects according to treatment actually received. All safety evaluations will be carried out on the safety set.

5. SUBJECT DISPOSITIONS

5.1. Dispositions

The number and percentage of subjects included in the analysis sets (safety, randomized, and full analysis sets) will be presented overall and by treatment group. Tables will indicate number of subjects who completed the study, number and percentage of subjects who completed the treatment, and the number of subjects who discontinued study and treatment for any of the following reasons:

- Does not meet I/E criteria
- Adverse Event
- Lab Results Clinically Significant
- Symptoms not consistent with protocol
- Lost to Follow-up
- Physician Decision
- Withdrawal by Subject/Withdraw Assent
- Death
- Other

These tables will be summarized by treatment group and overall. Disposition data will be summarized and provided in subject listings. The other reasons will be specified in the subject listings.

5.2. Protocol Deviations

A deviation from the protocol is an unintended or unanticipated departure from the procedures or processes approved by the sponsor and the Institutional Review Board (IRB)/ Independent Ethics Committee (IEC) and agreed to by the investigator. A significant deviation occurs when there is non-adherence to the protocol by the subject or investigator that results in a significant, additional risk to the subject. Significant deviations can include non-adherence to inclusion or exclusion criteria, enrolment of the subject without prior sponsor approval, or non-adherence to Food and Drug Administration (FDA) regulations or International Conference on Harmonisation (ICH) Good Clinical Practice (GCP) guideline. Relevant significant protocol deviations, with impacts to key safety and efficacy endpoints, will be summarized in a table by treatment group and overall. All protocol deviations will be displayed in a listing with significant and relevant deviations indicated.

6. DEMOGRAPHIC AND BASELINE CHARACTERISTICS

6.1. Demographic

Demographic characteristics include age, race, ethnicity, and enrollment by study center. Summary statistics by treatment group and overall will include counts and percentages for discrete variables, and number of subjects, mean, SD, median, minimum and maximum for continuous variables.

The following variables will be summarized by treatment group:

- 1) Continuous variable: age (years)
- 2) Categorical/discrete baseline and demographic variables: age [adolescent (13 to 17, inclusive), adult (18 to 22, inclusive)], ethnicity (Hispanic or Latino, Not Hispanic or Latino), race (American Indian or Alaska Native, Asian, Black or African-American, Native Hawaiian or Other Pacific Islander, White or Caucasian, or Other), enrollment by study center

6.2. Baseline Characteristics

Baseline characteristics include baseline body weight (kg), height (cm), alcohol use, Intelligence Quotient (IQ) by Stanford-Binet-5, Diagnostic and Statistical Manual of Mental Disorders (DSM-5) autism spectrum disorder criteria and Molecular FXS test.

Summary statistics by treatment group and overall will include counts and percentages for discrete variables, and mean, SD, median, minimum and maximum for continuous variables.

6.3. Medical History

6.3.1 General Medical History

General medical history will be coded by MedDRA Version 20.1 or higher and summarized by SOC and PT for each treatment group as well as overall. Subject medical history including specific details will be presented in a listing. Body system will be presented in descending order for all subjects (descending order by counts in the Total column).

6.4. Inclusion and Exclusion Criteria

All inclusion/exclusion information on screen fail subjects will be included in a by-subject listing. The listing will include whether all criteria were satisfied. For subjects who did not satisfy the criteria, the criterion number will be listed with the deviation, along with whether an exception was obtained.

7. TREATMENTS AND MEDICATIONS

7.1. Prior and Concomitant Medications and Procedures

Therapies, procedures, and medications started and stopped prior to the start of study treatment are referred to as prior therapies and prior medications, respectively. Therapies, procedures, and medications that started prior to treatment and continued on treatment as well as those that started during treatment are referred to as concomitant therapies and concomitant medications. In order to define whether a medication with missing start or stop dates is a concomitant medication, refer to the following additional criteria.

- if both the start and stop dates of a particular medication are missing, that medication will be considered concomitant;
- if the start date of a medication is missing and the stop date of that medication falls on or after the dose date, that medication will be considered concomitant;
- if the start date of a medication is missing and the stop date of the medication is prior to the dose date, that medication is considered not concomitant;
- if the start date of a medication is prior to the dose date and the stop date of the medication is missing, that medication is considered concomitant.

Prior and concomitant medications will be coded using the World Health Organization Drug Dictionary (WHO-DD) version December 2017 or later and will be classified by Anatomical Therapeutic Class (ATC) level 4 and preferred term (PT). For the presentation of concomitant medications, the ATC level 4 terms will be sorted alphabetically, and within ATC level 4 term, the PT will be used and presented by decreasing total frequency overall.

The number and percentage of subjects who took at least 1 medication during the double-blind period as well as the number and percentage of subjects who took each type of medication will be presented for each treatment group and overall.

Prior and concomitant medications and procedures will be presented in separate listings.

7.2. Study Treatments

7.2.1 Extent of Exposure

Total capsules taken will be derived as the total number of capsules dispensed minus the total number of capsules returned and the **duration of exposure** will be computed as the last dose date – first dose date +1 and will be presented in categories by age group. The duration of exposure will be categorized as follows: fewer than 1 day, 1 to < 8 days, 8 to < 15 days, 15 to < 43 days, 43 to < 85 days, and 85 days or more.

Subject listing of study treatment exposure will be provided.

7.2.2 Treatment Compliance

Treatment compliance of OV101 capsules will be summarized by treatment group over the entire treatment period. Compliance of placebo capsules will not be determined. Treatment compliance will be summarized by treatment group and overall.

Compliance (%) = (Actual number of OV101 capsules/ Expected number of OV101 capsules) *100%.

The actual number of active OV101 capsules taken will be derived as the sum of: 1) number of capsules dispensed at Baseline minus number of capsules returned at Week 6, and 2) number of capsules dispensed at Week 6 minus number of capsules returned at EOT.

The expected number of OV101 capsules will be derived by multiplying the daily dose (1, 2, or 3 active OV101 capsules for the 5, 10, or 15 mg groups, respectively) by duration of exposure (see Section 7.2.1).

The number of capsules dispensed and the number remaining will be tracked and recorded by individual bottle (labeled “Morning,” “Afternoon,” or “Evening”).

A subject is compliant if overall compliance is >=80%.

Dosing error specification (missed dose, capsule not taken in usual manner, extra capsules taken, wrong dose taken and others), time of dosing error (morning, afternoon, evening), and reasons for missed dose (e.g., forgot, subject refused, subject had side effects so parent decided to give a drug holiday and other reasons) for all dispensed capsules, both active or placebo, will be listed.

8. EFFICACY ANALYSES

The primary endpoint of the study is a safety endpoint and not an efficacy endpoint.

8.1. Secondary Efficacy Analysis

Descriptive statistics will be presented for continuous variables and their changes from baseline.

Exploratory modelling will be conducted on the efficacy variables using an MMRM to further investigate any trends evident in the descriptive statistics and to inform a future study. In case of exploratory modelling, the MMRM analysis will be performed on the change from baseline or the post-baseline result (depending on the endpoint) with age and baseline (if appropriate) as covariates, daily dosing regimen, visit, and age group as fixed effects, and visit by daily dosing regimen interaction. An unstructured covariance structure will be assumed. From this model, the least squares mean change from baseline and the corresponding 95% CI will be presented for each daily dosing regimen and the total (all regimens) at each post-baseline visit. The least squares mean difference and the corresponding 95% CI will be presented for each pairwise comparison between the 3 daily dosing regimens at each week. The least squares mean changes from baseline and corresponding 95% CIs will be plotted at each time point by daily dosing regimens.

In the case of a statistically significant age group main effect ($P<0.1$) in the MMRM or age effects deemed evident in descriptive statistics, the mean changes with 95% CI described above will be estimated for each age group separately as well as overall; this will be achieved by inclusion of an additional term (age by week by daily dosing regimen interaction) in the MMRM. In this case, these additional estimates and 95% CI will be tabulated and plotted.

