7.8.5 Exploratory Modelling

Post-hoc exploratory modelling may be conducted on selected variables using an MMRM to further investigate any trends evident in the descriptive statistics and to inform a future study.

In case of post-hoc exploratory modelling, the MMRM analysis will be performed on the change from baseline in the response variable with baseline as a covariate and fixed effects for daily dosing regimen, week, age group and week by daily dosing regimen interaction. An unstructured covariance structure will be assumed. From this model, the least squares mean change from baseline and the corresponding 95% CI will be presented for each daily dosing regimen and the total (all regimens) at each week. The least squares mean difference and the corresponding 95% CI will be presented for each pairwise comparison between the 3 daily dosing regimens at each week.

The least squares mean changes from baseline and corresponding 95% CIs will be plotted at each time point by daily dosing regimens.

In the case of a statistically significant age group main effect ($P<0.05$) in the MMRM or age effects deemed evident in descriptive statistics, the mean changes with 95% CI described above will be estimated for each age group separately as well as overall; this will be achieved by inclusion of an additional term (age by week by daily dosing regimen interaction) in the MMRM. In this case, these additional estimates and 95% CI will be tabulated and plotted.

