11. OTHER STATISTICAL ISSUES

11.1. Significance Levels

The primary objective of this study is safety and no power calculations for the efficacy analyses have been planned in the sample size justification.

No adjustment will be made for multiple testing, all p-values will be treated as exploratory and should be interpreted with caution.

All testing will be two-sided and conducted at 0.05 level of significance except for interactions, which will be tested at the 0.100 significance level.

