12. CHANGES COMPARED TO THE PROTOCOL

In Section 7.8.5 of the Protocol, p-value of 0.05 was applied as the level of significance in testing the effect of age group in MMRM. However, a p-value of 0.10 for age related interaction term was used in the model selection in the SAP.

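### SAP 8.1 puts both age and age group in the MMRM without defining or declaring the added term, and SAP 8.1, 11.1 and 12 do not agree on which age term is tested at 0.10

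*SAP*

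**What the plan says.** **Model.** Protocol 7.8.5 models change from baseline with "baseline as a covariate and fixed effects for daily dosing regimen, week, age group and week by daily dosing regimen interaction". Age group is the only age term. SAP 8.1 fits the MMRM "with age and baseline (if appropriate) as covariates, daily dosing regimen, visit, and age group as fixed effects", plus the visit-by-regimen interaction, so two age terms are named.

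**Gate for by-age estimates.** SAP 8.1 adds a three-way term and reports each age group separately "In the case of a statistically significant age group main effect" (P<0.1) "in the MMRM or age effects deemed evident in descriptive statistics". Protocol 7.8.5 has the same two routes, with P<0.05 for the first.

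**Level.** SAP 12 lists one change from the protocol: "a p-value of 0.10 for age related interaction term was used in the model selection in the SAP". SAP 11.1 says testing is two-sided and "conducted at 0.05 level of significance except for interactions, which will be tested at the 0.100 significance level".

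**Meaning of age.** SAP 8.1 gives no definition. SAP 6.1 has the entry "Continuous variable: age (years" and lists age group separately as categorical. SAP 4.3, however, uses the bare word for the category: "The randomization schedule will be stratified by age (13 to 17, inclusive; 18 to 22, inclusive". The three-way term in SAP 8.1 also says age, although its purpose is to give estimates per age group.

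**The concern.** Age group is the only stratification factor and the only subgroup named in advance (Protocol 7.7). The gate decides whether model-based estimates for adolescents and adults are tabulated and plotted. SAP 8.1 says the modelling will be done, where Protocol 7.8.5 says it may be, and its stated purpose is to inform a future study.

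If continuous age sits in the model beside age group, the age-group test no longer asks whether adolescents and adults differ. It asks whether there is a jump at 18 beyond a straight-line trend. A steady age trend would then leave the P-value gate at its false-positive rate, however steep the trend.

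Separately, a programmer following SAP 8.1 gates on a main effect at 0.10, and one following SAP 12 gates on an interaction at 0.10. The general rule in SAP 11.1 would put a main effect at 0.05. Different choices can lead to different by-age output from the same data.

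**Working it through.** **1. The plan's own figure.** The documents give no operating figure for the age gate and no efficacy power (SAP 11.1). Their only precision figure, the Wilson half-width for 6 of 30, reproduces: 1.96/(1 + 3.84/30) × √(0.2×0.8/30 + 3.84/(4×30²)) = 1.737 × 0.0800 = 13.9%. Only N is taken from there: 30 evaluable, 36 enrolled (SAP 4.2).

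**2. Assumptions.** Residual SD 1; equal arms and age groups; integer ages 13–22, uniform; baseline covariate; two-sided test at 0.10; age effects of 0.1 or 0.2 SD per year, or a step at 18.

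**3. Overlap of the two age terms.** Var(age) = (10² − 1)/12 = 8.25. Variance within a five-year group = (5² − 1)/12 = 2. VIF = 8.25/2 = 4.1, r = √(1 − 2/8.25) = 0.87.

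**4. Linear age effect.** If the mean response is a + b·age, a model with both terms fits it exactly with an age-group coefficient of 0. The test then rejects at alpha for any b. With age group alone, the group difference is 5b (mean ages 15 and 20), so 0.1 SD per year gives 0.5 SD.

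**5. Step at 18.** With age group alone, SE = √(4/N): 0.365 (N = 30) or 0.333 (N = 36). A 1-SD step has noncentrality 2.74 or 3.00, and the gate opens in 84.6% or 90.1%. With both terms the SE is multiplied by √4.125 = 2.03. Noncentrality falls to 1.35 or 1.48, and the gate opens in about 37% or 42%. Simulation gives slightly lower rates because the overlap varies between trials.

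**6. Simulation** (single visit, 6,000 trials per scenario), % of trials with age-group P<0.10:

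| Assumed age effect | Age group only, N = 30 / 36 | Both terms, N = 30 / 36 |
|---|---|---|
| None | 10.0 / 10.0 | 10.1 / 10.5 |
| Linear 0.1 SD/year | 36.1 / 40.7 | 9.8 / 10.5 |
| Linear 0.2 SD/year | 80.9 / 87.0 | 10.6 / 9.7 |
| Step 0.5 SD | 36.6 / 41.5 | 16.0 / 17.7 |
| Step 1.0 SD | 83.6 / 89.5 | 34.2 / 38.9 |

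Other age spreads (VIF 3.2 to 7.4): with both terms, 9.5–10.8% for a linear effect and 23–46% for a 1-SD step. Three visits, within-subject correlation 0.5–0.8: linear 0.1 gives 40–54% against 9–10%, and a 1-SD step 87–97% against 38–52%.

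**7. The level.** With age group alone, N = 30 and a correlation of 0.3 between response and age (0.3/√0.91/2.872 = 0.11 SD per year), the gate opens in 41% at 0.10 and 30% at 0.05.

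**8. Main effect or interaction.** SAP 12 does not say which interaction it means. Taking age group by regimen at 0.10:
- Linear or step age effect common to all arms: the interaction test opens in about 10%, its correct type I error since no interaction exists.
- Arm effects of −0.5/0/+0.5 SD reversed between age groups: noncentrality = cell size × 4 × 0.25 = 5 (N = 30) or 6 (N = 36), and the interaction test opens in 57–67%. The main-effect gate opens in about 7–8%.

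**The case against.** The loss of power exists only if age is continuous, and SAP 8.1 never says so. SAP 4.3 and the three-way term both use the bare word for the category. If that was meant, the extra term is redundant and the whole one-term against two-term comparison falls away. This stands. A reader might infer that the gate is certainly broken, but the documents show only that it is broken on one plausible reading. The split between covariate and fixed effect, and SAP 6.1, favour that reading without settling it.

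The P-value is also not the only route. Age effects judged evident in the descriptive statistics open the by-age estimates too, and plots and listings identify age group (Protocol 7.7, SAP 4). The simulated rates leave this route out, so they describe the P-value gate and not the chance that by-age estimates are reported. The descriptive route has no criterion, so it does not replace a defined gate.

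The effect sizes are assumed, because the documents give none. The alpha-only result under a linear effect does not depend on them; the other rates do.

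It may be said that the omission from SAP 12 is no breach: Protocol 7.8 lets the SAP modify the analysis, and SAP 1 promises to flag only substantial differences. That is arguable. But SAP 12 does describe the change of level, and its description does not match SAP 8.1.

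**Conclusion.** The point holds as an unclear specification and an internal contradiction. SAP 8.1 names an age term that the protocol model lacks, does not define it, and SAP 12 does not declare it. If it is continuous, and under the assumptions above, the P<0.1 gate opens in about 10% of trials for any linear age effect (36–41% with age group alone at 0.1 SD per year). For a 1-SD step at 18 it opens in 34–39% instead of 84–90%. If it means age group, the gate is unaffected.

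The conflict over the 0.10 level holds on either reading: main effect in 8.1, interaction in 12, and 0.05 for a main effect under 11.1.

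Two stronger inferences are not supported. First, the documents do not show that an interaction gate would be wrong. The main effect detects age differences in mean change and the interaction detects age differences in dose effect, so the choice is the sponsor's. Second, nothing here touches the primary safety endpoints or the descriptive by-regimen results. The effect is confined to exploratory, unadjusted by-age efficacy estimates. The correction should be made because it is nearly free and removes a choice now left to the programmer.

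**What to change.** - SAP 8.1: delete age from the covariates so that age group, the stratification factor, is the only age term. If continuous age is kept, test the age-group gate in a model without it.
- SAP 8.1: write the added term as age group by visit by daily dosing regimen.
- Choose one gate term and one level, and state them identically in SAP 8.1, 11.1 and 12. If the age-group main effect at 0.10 is kept, correct SAP 12 to name that term and list it as an exception in 11.1.
- SAP 12: declare any remaining departure from the Protocol 7.8.5 model.

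The cost is SAP wording and one model term, with no new data. The downside of dropping continuous age is that a linear age trend within each age group is not adjusted for. A main-effect gate also stays insensitive to dose effects that reverse by age, and an interaction gate to an age difference common to all arms.
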